10.0 EVALUATION DURING TREATMENT/INTERVENTION

During the treatment patients will be seen in clinic every 4 weeks (prior to every cycle) and more frequently if required by primary BMT attending. All patients will be closely monitored and evaluated as per MSKCC BMT standard of care guidelines. Evaluations may be withheld if the treating physician feels that there is a strong contra-indication to perform the study (e.g. patient has relapsed or is terminally ill). Also, additional tests will be performed as clinically indicated. Study specific assessment schedule listed in table below.

Schedule of Study Assessments

Procedures	Pre-Treatment	Post Treatment Start					
		C1 & C2			C3+		
		D1	D8	D15	D22	D1	D15
Window	45	(+/-) 7	(+/-) 3	(+/-) 3	(+/-) 3	(+/-) 7	(+/-) 3
Eligibility	X						
Informed consent	X						
History/Physical	X						
Pregnancy Test (1)	X	X					X
Blood Chemistry/CMP (2)	X	X					X
CBC (2)	X	X	X	X	X	X	X
Echo- if no new symptoms, pretransplant is adequate	X						
Toxicity assessment (3)		X				X	
Correlative studies – Peripheral blood for Tregs expression studies (4)		X*					

Procedures	Post Transplant				
	100 days	6 months	12 months	18 months	24 months
Window	(+/-) 21	(+/-) 14	(+/-) 14	(+/-) 14	(+/-) 14
Chimerism (Peripheral Blood) (5)	X	X	X	X	X
Bone marrow aspirate and/or biopsy (6)	X	X	X	X	X
Peripheral blood lymphocytes phenotyping and in-vitro response (7)	X	X	X	X	X
Correlative studies - BM sample for methylation assays, flow studies for MRD (8)	X	X	X	X	X
Correlative studies – Peripheral blood for Tregs expression studies			X	X	

*Peripheral blood samples will be collected prior to start of Azacitidine treatment on C1D1 only

- (1) Pregnancy Test – Not required for Cycle 1 Day 1 if done at screening, but required for Day 1 of each subsequent cycle for FCBP.
- (2) CBC – checked weekly during the first 2 cycles, and if stable, every 2 weeks with subsequent cycles. Outside CBC results will be accepted for D8, 15 and 22 of C1 and C2 and for D15 of subsequent cycles. CBC/Chemistry must result prior to IP administration on or within 7 days of Day 1 of each cycle. If a CBC is performed within overlapping windows for two time-points, it is not necessary to repeat unless clinically indicated.
- (3) Toxicity Assessment - Not required for Cycle 1 Day 1, but required for Day 1 of each subsequent cycle or within 7days of Day 1 of each cycle. Patients who pass away, complete treatment or end treatment before the start of the next cycle will have toxicities captured at the end of the last cycle started.
- (4) Peripheral blood samples (2 GTT) will be collected and stored at HOTB prior to start of Azacitidine treatment on C1D1 and at 12 and 18 months post-transplant
- (5) Peripheral blood will be checked for neutrophil, B cells, and T cell chimerism
- (6) In the first year bone marrow tests will be performed to assess disease status by morphology, cytogenetics, and molecular as per BMT standard of care time-points. Following the first year these studies will be performed at 18 and 24 months post transplant.
- (7) Peripheral blood will be checked for lymphocytes phenotyping as well as in-vitro response to standard panel of mitogens as per BMT standard of care.
- (8) Correlative studies include global and specific genes methylation status, Fluorescence activated cell sorting (FACS) and FISH assays will be used to assess for residual involvement for the HSC compartment

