4.3 Intervention

5'-azacitidine will be given at a low dose of 32mg/m² S.C for 5 days every 28 days (a cycle). Dose de-escalation will be permitted for hematologic and non- hematologic toxicities.

Patients will start taking the study drug between days 60-120 post TCD allogeneic hematopoietic stem cell transplant and up to a year post-transplant or until there is a toxicity that requires cessation of therapy. Therefore patients will get between 8-10 cycles. Patients who come off-study for reasons unrelated to toxicities before completing 4 cycles will be replaced. Since most cases of relapse occur early post transplant, in the first year, this is the most appropriate time to intervene. Treatment will start as soon as possible.

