8.1 PRETREATMENT EVALUATION

The patient will undergo comprehensive medical evaluation after stable engraftment has been documented. This evaluation includes:

1. Complete physical exam and medical history
2. Bone marrow tests post HSCT will be performed to determine remission status by morphology, cytogenetics and molecular studies (if indicated) and chimerism as part of routine post transplant assessments. At the same time, bone marrow sample will also be taken for baseline correlative studies under the biospecimen protocol. Any bone marrow sample collected prior to starting treatment with Azacitidine can be used as baseline for correlative studies.
3. Complete blood counts (CBC)
4. Complete metabolic panel
5. Pregnancy test will be checked for women at child bearing age prior to initiation of treatment

6. Cardiac: Adequate cardiac function measured by LVEF>50%. If asymptomatic, pre-transplant echocardiogram is adequate. If symptomatic, echocardiogram needs to be repeated.

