9.1 TREATMENT/INTERVENTION PLAN

1. 5'-azacitidine will be given at a dose of 32mg/m² for 5 consecutive days subcutaneously. Treatment will be given every 28 days (cycle). Treatment will be given up to a year post transplant.
2. CBC will be checked weekly during the first 2 cycles, and if stable every 2 weeks with following cycles. CBC results from tests performed externally will be accepted for Days 8, 15, and 22 of C1 and C2 and Day 15 of subsequent cycles. Comprehensive metabolic panel will be checked at the beginning of every cycle.
3. Pregnancy test will be checked for women at child bearing age prior to start of each cycle.
4. Bone marrow studies (day 100, and 6, 12, 18 and 24 months post transplant) for assessment of disease status and chimerism. Peripheral blood chimerism status at day 100, and 6, 12, 18 and 24 months post transplant will be tested as part of routine post transplant evaluation
5. Peripheral blood lymphocytes phenotyping and in-vitro response to standard panel of mitogen will be assessed as part of routine post transplant assessment
6. Bone marrow samples for correlative studies will be tested at the same time that patients are undergoing routine BM studies. These tests are considered experimental.
7. Peripheral blood samples for correlative studies will be collected prior to start of Azacitidine treatment on C1D1 and at 12 and 18 months post transplant. These tests are considered experimental.

Dose modifications

Event	Modification
ANC <1000/uL for > 4 days.	Drug held until resolved (ANC 1500) and up to 60 days. If after 60 days there is no neutrophils recovery the treatment will be permanently discontinued.
• If by next cycle ANC is 1000-1500, not G-CSF dependent	Resume therapy with 50% dose reduction
• If by next cycle ANC fully recovered, >1500 not G-CSF dependent	Resume full therapy dose
Platelets <10,000/uL for > 4 days, or if transfusion dependent to keep count>10,000/ uL	Drug held until resolved (>50,000) and up to 60 days.

• If by next cycle Platelets are 10,000-50,000, not transfusion dependent	Resume therapy but with 50% dose reduction
• If by next cycle Platelets >50,000	Resume full therapy dose
Hemoglobin < 8g/dL for > 4 days or if transfusion dependent	Drug held until resolved (> 8g/dL) and up to 60 days.
• If by next cycle hemoglobin >8g/dL	Resume full therapy dose
Hepatic toxicity – Drug related grade 3-4	Drug stopped

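### Footnote 1 of the Section 10 schedule lets a screening pregnancy test up to 45 (presumably days) old clear the first azacitidine dose, although CBC/chemistry for that dose must be within 7 days

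*Combined protocol and SAP*

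**What the plan says.** All references are to the combined protocol and SAP.

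- **Section 10.0, schedule of assessments.** The Pre-Treatment column includes a pregnancy test and has a window of 45, with no unit. The Day 1 columns have a window of plus or minus 7.
- **Section 10.0, footnote 1 (pregnancy test).** "Not required for Cycle 1 Day 1 if done at screening, but required for Day 1 of each subsequent cycle".
- **Section 10.0, footnote 2 (blood counts and chemistry).** "CBC/Chemistry must result prior to IP administration on or within 7 days of Day 1 of each cycle". Cycle 1 is not exempted.
- **Section 8.1, item 5.** "Pregnancy test will be checked for women at child bearing age prior to initiation of treatment".
- **Section 9.1, item 3.** "Pregnancy test will be checked for women at child bearing age prior to start of each cycle".
- **Section 10.0, opening paragraph.** "Also, additional tests will be performed as clinically indicated".
- **Section 4.3.** "Patients will start taking the study drug between days 60-120 post TCD allogeneic hematopoietic stem cell transplant". The same section asks for treatment to begin promptly.

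**The concern.** The waiver in footnote 1 sets no age limit on the screening test, so the only limit is the 45 in the Pre-Treatment column. A woman who conceives after screening could receive her first course without the plan requiring another test. The blood results used to release that same dose must be no more than a week old.

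The plan already treats pregnancy as worth rechecking in these patients, because it requires a new test before every later cycle. The first exposure is the one point where an older result is accepted. What is at stake is individual safety and not the trial's inference: an unrecognised early pregnancy exposed to a drug that Section 3.3 describes as a DNA methyltransferase inhibitor incorporated into DNA and RNA.

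**Working it through.** The plan states no figure to reproduce. The check sets the timing rules side by side.

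**Inputs**
- Pre-Treatment window: 45 (Section 10.0 schedule). Days is an assumption, and the natural one, because footnotes 2 and 3 give the corresponding 7 in days.
- Limit for blood counts and chemistry: 7 days, explicit in footnote 2.
- Day 1 window: plus or minus 7 (Section 10.0 schedule).
- Cycle length: 28 days (Section 9.1, item 1).
- Permitted start: days 60 to 120 after transplant (Section 4.3).

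**Step 1: oldest permitted result at each dose**

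| Dose | Check | Oldest result | Basis |
|---|---|---|---|
| Cycle 1 | Pregnancy test | 45 days | Window plus footnote 1 waiver |
| Cycle 1 | CBC/chemistry | 7 days | Stated in footnote 2 |
| Later cycles | Pregnancy test | 7 days | Inferred |

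The last row combines three things: footnote 1 ties the test to Day 1, the Day 1 window is plus or minus 7, and Section 9.1 item 3 puts the test before the cycle starts, which removes the plus side. No sentence states 7 days for this test. In the extracted table the Cycle 3 and later pregnancy mark falls under Day 15. That may be a conversion artefact, so the timing here is taken from footnote 1 and Section 9.1.

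**Step 2: size of the gap at the first dose**
- 45 − 7 = 38 days, against the stated CBC/chemistry limit.
- 45 / 28 = 1.6 cycles, so the permitted age exceeds a full treatment cycle.

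**Step 3: does another rule shorten the 45?**
- Section 8.1 item 5 and Section 9.1 item 3 require a test beforehand but set no maximum age. A 45-day-old test satisfies both.
- The allowance for additional tests permits a retest but does not require one.
- The start window may shorten it. If screening cannot occur before day 60, the maximum age is the smaller of 45 and (start day − 60): 0 at day 60, 7 at day 67, 30 at day 90, and 45 from day 105.
- Section 8.1 ties the evaluation only to engraftment ("The patient will undergo comprehensive medical evaluation after stable engraftment has been documented"). If screening may therefore precede day 60, 45 is permitted at any start day.

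**Step 4: dose holds**

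The neutrophil rule reads "Drug held until resolved (ANC 1500) and up to 60 days". A hold does not create the same gap, because the resumed cycle still needs its own test before it starts.

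**The case against.** The strongest case for leaving the text alone has four parts.

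1. *The later-cycle comparator is not a written rule.* This stands. The authors wrote 7 days into footnotes 2 and 3 but not into footnote 1, and plus or minus 7 may be only a visit window. The comparison with CBC/chemistry at Cycle 1 is the explicit one and does not depend on this inference.
2. *Counts and chemistry serve another purpose.* They drive holds and dose reductions under Section 9.1, so they must be current, and a different window for a screening test is a design choice. This is fair as to motive. It does not explain why a fresh pregnancy test is wanted before each later cycle but not before the first.
3. *The risk may be negligible.* The trial has 32 patients aged 1 to 75, all recently given myeloablative conditioning, and treatment is meant to start promptly. This largely stands. The documents give no number of women of childbearing potential, no chance of conception and no usual interval from screening to dosing. The birth-defect entry in Section 17.3 belongs to a generic definition of seriousness and adds little. The low-conception argument would, however, apply also to the later cycles, where the plan retests.
4. *Other safeguards may exist.* Institutional transplant guidelines are referred to but not shown, and consent pages were removed before review. No claim is made about either.

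A reader might also infer that footnote 1 contradicts Sections 8.1 and 9.1. It does not, because neither section sets a maximum age.

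**Conclusion.** The point holds as a cheap safety improvement. As written, a pregnancy test up to 45 days old can clear the first dose, against 7 days for CBC/chemistry at that dose, a gap of 38 days. This assumes that the unprinted unit is days. The 45 is a permitted maximum, not the expected interval, and it may be shorter for early starts if screening cannot precede day 60.

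Two stronger readings are not supported. One is that the plan states a 7-day limit for later pregnancy tests; that limit is inferred. The other is that counting the permitted start days on which an old test is allowed gives the share of patients affected; such a count describes the calendar, not patients or likely starts.

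The number of women at risk is unknown and may be close to zero. The primary endpoint and the error rates are unaffected.

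**What to change.** Replace footnote 1 with wording such as: *For FCBP, a negative pregnancy test must result before dosing and within 7 days before Cycle 1 Day 1; a screening test counts only if it falls in that window.* The requirement for Day 1 of each later cycle should be kept alongside it. Sections 8.1 and 9.1 can stay as they are.

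The cost is one footnote change and at most one additional routine test per woman of childbearing potential screened more than 7 days before dosing. It can be done with the CBC/chemistry already required within 7 days, so no visit is added.

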6.2 Subject Inclusion Criteria

1. Age: pediatrics and adults patients – 1 year old-75 years old.
2. Karnofsky performance status >=60% for patients >16yo and Lansky performance status >=60% for patients ≤16yo
3. Stable blood counts (ANC>1000/uL, Hb>8gr/dL, Plt>50,000/ uL) not supported by transfusions.
4. Renal: Serum creatinine <1.5 ULN
5. Hepatic: <3xULN ALT and <1.5 total serum bilirubin, unless there is congenital benign hyperbilirubinemia.
6. Cardiac: Adequate cardiac function measured by LVEF>50%. If asymptomatic, pre-transplant echocardiogram is adequate. If symptomatic, echocardiogram needs to be repeated.
7. Each patient must be willing to participate as a research subject and must sign an informed consent form.

Patients who were treated with 5'-azacitidine without response prior to transplant would be eligible to participate on this protocol.

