6.3 Subject Exclusion Criteria

Patients will be excluded from the trial if at time of enrollment:

1. Active uncontrolled bacterial, fungal or viral infection.
2. Evidence of uncontrolled graft-versus-host disease.
3. Pulmonary: new onset hypoxia
4. Known or suspected hypersensitivity to 5'-azacitidine or mannitol.
5. Evidence of residual disease either by increased blasts count (>5%) or persistence of previous known cytogenetics abnormalities.
6. Peripheral blood neutrophil chimerism: less than 95% donor.

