11.1 TOXICITIES/SIDE EFFECTS

Toxicities will be graded according to NCI CTAE version 4.0 grades 3-4 only, except grades 1-4 hepatic toxicity (increased AST, ALT, alkaline phosphatase and bilirubin) and grades 1-4 GI toxicity (nausea, vomiting, diarrhea). The side effects and toxicities related to 5-azacitidine are listed below.

5'-azacitidine

Likely

- Nausea
- Vomiting
- Diarrhea
- Constipation
- Lowered white blood cell count that may lead to infection
- Lowered platelet count that may lead to an increase in bruising or bleeding
- Lowered red blood cells that may cause anemia, tiredness, or shortness of breath
- Chest pain
- Fever
- Fatigue and weakness
- Headache
- Dizziness
- Bruising
- Rash
- Dry skin
- Skin nodules
- Erythema
- Weight loss
- Abdominal pain
- Loss of appetite
- Joint pain
- Muscle Pain
- Breathlessness
- Upper respiratory tract infections as well as infections of the throat and sinuses
- Pneumonia

- Injection site bruising, pain or reaction
- Anxiety
- Insomnia

Less Likely:

- Abnormal heart beat
- Fainting spells
- Skin infections
- Upper abdominal pain
- Bleeding from the gums
- Difficulty eating
- Hemorrhoids
- Pain when urinating
- Urinary tract infection
- Muscle cramps
- Wheezing
- Fluid on the lungs
- Increased sweating
- Night sweats

Rare But Serious:

- Convulsions
- Anaphylaxis
- Bone marrow depression
- Congestive Heart Failure
- Stupor
- Coma

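### No graded toxicity assessment is required before the first dose, so low-grade GI symptoms present at entry cannot be reliably separated from new ones

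*Combined protocol and SAP*

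**What the plan says.** The toxicity row of the Section 10.0 schedule, "Toxicity assessment (3", is marked under Day 1 of cycles 1 and 2 and Day 1 of later cycles. Nothing is marked under Pre-Treatment. Footnote (3) then removes the cycle 1 mark: "Toxicity Assessment - Not required for Cycle 1 Day 1, but required for Day 1 of each subsequent cycle". It allows a 7-day margin and captures toxicity at the end of the last started cycle if treatment ends early.

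Section 11.1 limits grading to grades 3-4, "except grades 1-4 hepatic toxicity (increased AST, ALT, alkaline phosphatase and bilirubin) and grades 1-4 GI toxicity (nausea, vomiting, diarrhea". GI and hepatic findings are thus the only ones for which low grades are collected.

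On who may enter:
- Section 6.1, item 5, admits patients 60 to 120 days after transplant.
- Section 6.2, item 5, sets "Hepatic: <3xULN ALT and <1.5 total serum bilirubin", which allows ALT above normal.
- Section 6.3, item 2, excludes "Evidence of uncontrolled graft-versus-host disease", which leaves controlled GvHD admissible.

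On what is measured before dosing:
- Section 8.1 requires a history and physical and a "Complete metabolic panel".
- The schedule marks the history and physical only under Pre-Treatment, with a window of 45 (no unit printed).
- The row "Blood Chemistry/CMP (2" is marked under Pre-Treatment and also under Day 1 of cycles 1 and 2.
- Footnote (2) adds: "CBC/Chemistry must result prior to IP administration on or within 7 days of Day 1 of each cycle". It makes no exception for cycle 1.

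**The concern.** In a single-arm trial the patient's own pre-dose state is the natural comparator for low-grade adverse findings. These patients are a few months past a myeloablative, T cell depleted transplant, and the entry criteria leave room for ongoing nausea, diarrhea or a raised ALT. If such a symptom is first graded after cycle 1, a patient whose mild diarrhea is unchanged since entry gets the same entry on the toxicity form as one in whom it began on azacitidine. No section defines a treatment-emergent toxicity or says how to handle a finding present at entry.

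What is at stake is the reading of the low-grade GI data that the plan chose to collect, and to a lesser extent the hepatic data. A reader of the results could not tell how much of the reported GI toxicity was there before treatment.

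**Working it through.** The plan gives no figure on this point, so the check is mainly a comparison of what exists before the first dose with what is graded afterwards.

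| Item | Graded from (11.1) | Available before first dose | Pre-dose grade required? |
|---|---|---|---|
| Nausea, vomiting, diarrhea | Grade 1 | History and physical, window 45 (8.1, 10.0) | No |
| AST, ALT, alkaline phosphatase, bilirubin | Grade 1 | Chemistry at Pre-Treatment and within 7 days of Day 1 of cycle 1 (8.1, 9.1 item 2, 10.0 footnote 2) | No, but the values exist |

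**GI.** The three symptoms have no laboratory trace. A history may mention them, but nothing asks for a grade, and the scheduled history need not be close to the first dose. A grade that was never recorded cannot be rebuilt reliably. The gap is real.

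**Hepatic.** The four items are laboratory values. If the metabolic panel includes all four, as is usual (the documents do not list its contents), each patient has a value close to the first dose that can be graded later. An unchanged ALT can then be told from a new rise. What is missing is an instruction to use these values as the reference.

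**Where the grades are used.**
- Primary endpoint (14.1): relapse by two years. No toxicity grade enters.
- Stopping boundaries (14.1): neutropenia, thrombocytopenia and treatment-related mortality. No GI or hepatic grade enters.
- Safety objective (2.1) and its tabulation (14.1): transfusions, bleeding, serious infections and G-CSF use. No GI or hepatic grade is named.
- Dose-modification table (9.1): hepatic rows apply to drug-related events and name no reference grade. There is no GI row.

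The effect is therefore confined to descriptive GI and hepatic toxicity results.

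**Size.** Let e be the true treatment-emergent rate, b the share of patients with a GI symptom of grade 1 or higher at C1D1, and p the fraction of those symptoms that persist to C2D1 and are counted. If entry and emergent symptoms are independent:

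recorded rate = 1 − (1 − e)(1 − b·p), overstatement = (1 − e)·b·p.

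None of e, b or p is in the documents. Taking e = 0.15 and b = 0.10 to 0.40 purely as assumptions:
- p = 1: 1 − 0.85 × 0.90 = 23.5% to 1 − 0.85 × 0.60 = 49%, an overstatement of 8.5 to 34 points.
- p = 0 (symptoms resolve or are attributed elsewhere): recorded rate 15%, no overstatement.

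With e = 0.10 and p = 1 the recorded rate is 1 − 0.90 × 0.90 = 19% to 1 − 0.90 × 0.60 = 46%. The p = 1 figures are worst cases under assumed inputs. The range from none to large shows that the documents do not settle the size.

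**The case against.** The strongest reply is that the plan is less blind than the empty cell suggests. Chemistry is required before cycle 1 dosing, so hepatic abnormalities at entry are measured. Each patient has a history and physical and is seen in clinic before every cycle, so symptoms are likely to be known to the physician. The hepatic dose rows apply only to drug-related events, and serious adverse event reports carry a relationship field and start at consent (17.3). On the hepatic side this reply largely stands. For low-grade GI symptoms it does not, because clinical awareness is not a recorded grade, and a relationship judgment is weaker without one.

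Three stronger readings are tempting, and the documents do not support them:
- **That entry findings will be read as azacitidine toxicity.** This is an inference. No section says that every finding after cycle 1 is counted as drug toxicity. The text supports only that the two cannot be reliably separated for GI symptoms.
- **That the safety objective cannot be met.** Section 2.1 ties that objective to transfusions, bleeding, serious infections and G-CSF use, and 14.1 tabulates those items. GI and hepatic grades are not part of it.
- **That misattribution shifts who is evaluable or replaced.** Section 13.0 does turn on whether toxicity is treatment-related. But no rule leads from a low-grade GI finding to stopping treatment, and the hepatic rule that stops the drug concerns grades 3-4 of laboratory values that have a pre-dose measurement.

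**Conclusion.** The concern holds for GI symptoms and, in a weaker form, for hepatic values. Nausea, vomiting and diarrhea are collected from grade 1 with no graded pre-dose reference, because footnote (3) expressly waives the assessment that would have supplied one. Hepatic reference values exist, but their role in grading is unstated.

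The consequence is limited to descriptive results in a 32-patient cohort. No sample size, error rate, stopping boundary or named safety tabulation changes. The amount of overstatement, if any, depends on how common and how persistent low-grade GI symptoms are at entry and how attribution is made, and the documents give none of these. The conclusion rests on the schedule as printed, with the Pre-Treatment toxicity cell empty, and on the absence of any baseline-adjusted definition in Sections 10.0, 11.1 and 14.1. The correction is worth making because it is cheap and a missing baseline grade cannot be recovered afterwards.

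**What to change.** 1. Change footnote (3) in Section 10.0 so that the graded toxicity assessment is required at C1D1, before the first dose. The schedule already marks Day 1 of cycles 1 and 2, so only the waiver has to go.
2. State that the hepatic baseline is graded from the chemistry already required within 7 days of Day 1 of cycle 1.
3. Add to 11.1 and 14.1 that GI and hepatic toxicity is reported as worsening from the C1D1 grade, and show the C1D1 grades beside the on-study ones.

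The cost is one extra toxicity form per patient at a visit that already takes place, plus a sentence in each of the two sections. No visit or procedure is added, and the design, error rates and dose-modification table are untouched. For any patients already treated, the hepatic baseline can be graded from stored results. Their GI baseline should be shown as not recorded rather than assumed to be zero.
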